### **8.3. Extension Eligibility**

Patients must complete 12 weeks of treatment in Part 1, or 48 weeks of treatment in Part 2, have no significant protocol deviations that would, in the opinion of the investigator, deem the patient unsuitable for enrollment in the Extension phase of the study, and continue to meet inclusion and exclusion criteria as specified in [Appendix 1](#).

### **8.4. Patient Rescreening**

Patients may repeat the screening procedures to qualify for the study if they have:

- Used antioxidant supplements, including but not limited to idebenone, coenzyme Q10, nicotinamide, and vitamin E above the recommended daily allowance, within 14 days prior to Study Day 1 (rescreening may be performed 14 days or more after discontinuation of supplement)
- Used anticoagulant therapy within 30 days prior to Study Day 1 (rescreening may be performed 30 days or more after discontinuation of anticoagulant therapy)
- Participated in any other interventional clinical study within 30 days prior to Study Day 1 (rescreening may be performed 30 days or more after completion of the clinical study)
- An abnormal laboratory test value that may normalize, in the opinion of the investigator (rescreening may be performed once test value is within normal range)
- Modified their exercise regimen within 30 days prior to Study Day 1 (rescreening may be performed 30 days or more after modification of exercise regimen)
- Taken any of the following drugs within 7 days prior to Study Day 1 (rescreening may be performed 7 days or more after discontinuation of the drug):
  - Sensitive substrates for cytochrome P450 2C8 or 3A4 (e.g., repaglinide, midazolam, sildenafil)

- Moderate or strong inhibitors or inducers of cytochrome P450 2C8 or 3A4 (e.g., carbamazepine, phenytoin, ciprofloxacin, grapefruit juice)
- Substrates for p-glycoprotein transporter (e.g., ambrisentan, digoxin)
- Failed screening because of operational challenges (rescreening may be performed no fewer than 2 weeks from the date of screen failure)
- Failed screening because of mFARS (the absolute difference in mFARS was  $\geq 4.5$  points between Screening and Day 1)

Patients may repeat the screening procedures once to qualify for Parts 1 and 2 of the study. For the Extension, patients may be rescreened at the discretion of the Sponsor, following discussion with the investigator site.

## **8.5. Patient Discontinuation and Termination**

Patients have the right to withdraw from the study at any time for any reason, without prejudice to their medical care. Furthermore, the investigator may discontinue a patient from study drug or terminate the patient from the study. The reason for a patient's withdrawal or discontinuation from the study will be recorded in the electronic case report form (eCRF).

### **8.5.1. Patient Discontinuation Criteria**

Discontinuation refers to a patient stopping administration of study drug. Reasons for study drug discontinuation may include the following:

- Occurrence of an AE or change in medical status that leads the investigator to be concerned about the patient's welfare
- Protocol violations
- Administrative reasons (e.g., inability to continue)
- Sponsor termination of the study
- Voluntary withdrawal
- Pregnancy during the study
- Investigator unblinding

Patients must permanently discontinue study drug if any of the following occur:

- ALT or AST  $> 8X$  ULN;
- ALT or AST  $> 5X$  ULN for more than 2 weeks;
- ALT or AST  $> 3X$  ULN and TBL  $> 2X$  ULN
- ALT or AST  $> 3X$  ULN with the appearance of fatigue, nausea, vomiting, right upper quadrant pain or tenderness, fever, rash, and/or eosinophilia ( $> 5\%$ ).

Patients who are discontinued from study drug in Part 1 or Part 2 should still complete all study visits and undergo all scheduled study assessments, if possible.

**8.5.2. Patient Termination Criteria**

Termination refers to a patient stopping study drug and all study assessments and visits. Reasons for study termination include the following:

- Administrative reasons (e.g., inability to continue, lost to follow-up)
- Death
- Withdrawal of consent

Patients who terminate the study for any reason may not re-initiate study drug or study assessments at any time.

## 9. TREATMENT OF PATIENTS

### 9.1. Description of Study Drug

Part 1: Depending on cohort dose level (or doses selected for part 2) patients will ingest up to 6 capsules of study drug (1 from each bottle included in study treatment kit) daily throughout the study; study drug is described in Section 10.1. Treatment kits containing up to 160 mg of RTA 408 or placebo will include 4 bottles, each containing 30 count of either active or placebo capsules. Treatment kits containing greater than 160 mg of RTA 408 or placebo will be comprised of 6 bottles, each containing 30 count of either active or placebo capsules. To maintain the study blind, treatment kits used in Part 2 will all include the same number of bottles.

Part 2: Patients will ingest 3 capsules daily throughout the study; study drug is described in Section 10.1. Treatment kits containing RTA 408 or placebo will include 3 bottles, each containing 30 count of either active (RTA 408 50 mg) or placebo capsules. Patients may receive more than 1 treatment kit during dispensation to provide sufficient study drug until their next planned dispensation.

Extension: Patients will ingest 3 capsules daily throughout the extension; study drug is described in Section 10.1. Treatment kits containing RTA 408 will include 3 bottles, each containing 30 count of active (RTA 408 50 mg) capsules. Patients may receive more than 1 treatment kit during dispensation to provide sufficient study drug until their next planned dispensation.

The Sponsor will provide sufficient quantities of study drug to allow for completion of the study.

#### 9.1.1. Management of Elevated Transaminase Levels (ALT and/or AST)

In ongoing clinical trials with RTA 408, transient increases in transaminases and GGT levels have been observed in some patients (refer to the Investigator's Brochure for additional information). Transaminases should be monitored using data from the scheduled lab draws in Part 2 and the extension. Nearly all instances of elevated transaminases are expected to be asymptomatic. Transaminase levels (as well as TBL, GGT, ALP) will be checked within 48 to 72 hours during an unscheduled visit if the following occurs:

- ALT or AST levels > 3X ULN.

Testing will be repeated every 72 to 96 hours until transaminase levels are below 3X the ULN for at least one week or until the patient withdraws consent.

Study drug administration will be permanently discontinued if any of the following occurs:

- ALT or AST > 8X ULN;
- ALT or AST > 5X ULN for more than 2 weeks;
- ALT or AST > 3X ULN and (TBL > 2X ULN);
- ALT or AST > 3X ULN with the appearance of fatigue, nausea, vomiting, right upper quadrant pain or tenderness, fever, rash, and/or eosinophilia (> 5%).

The hepatobiliary tree must be visualized (*e.g.*, ultrasound, MRI) and assessed if a patient discontinues taking study drug secondary to elevated transaminase levels. Additional tests/studies may be warranted depending on the clinical presentation.

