**Table 5: Extension Schedule of Assessments**

Study Day/Week	Screening a	Day 1 b	Week 2 (telephone)	Week 4	Week 10	Week 16	Week 24 + Every 24 Weeks	End of Study
Day Relative to First Dose in Extension	-30 to -1	1	14 (±3 days)	28 (±3 days)	70 (±3 days)	112 (±3 days)	168, 336, 504, etc. (±14 days)	Within 30 days after last dose
Informed consent	X							
Inclusion/Exclusion	X	X						
Pes cavus assessment	X							
Medical history	X							
Adverse event collection		X c	X	X	X	X	X	X
Prior and Concomitant medications	X	X	X	X	X	X	X	X
Weight and BMI	X	X d		X	X	X	X	X
Vital sign measurements	X	X d		X	X	X	X	X
Physical examination	X	X d		X	X	X	X	X
Height	X			X j				
Echocardiogram e	X							
Electrocardiogram e	X							
Clinical Chemistry	X			X	X	X	X	X
Hematology	X			X	X	X	X	X
Urinalysis and microscopy	X			X	X	X	X	X
BNP and NT-proBNP f	X			X	X	X	X	X
Hepatitis B and C and HIV 	X							
Pregnancy test WOCBP h	X	X		X	X	X	X	X
Dispense study drug		X		X			X	
Study drug return and pill count				X			X	X
Neurologic FARS		X					X	X
Activities of Daily Living		X					X	X
Patient Global Impression of Change							X	
Clinical Global Impression of Change							X	
25-foot Timed Walk Test		X					X	X
9-Hole Peg Test		X					X	X

Abbreviations: BMI=body mass index; BNP= B-type natriuretic peptide; FARS=Friedreich's ataxia rating scale; HIV=human immunodeficiency virus; NT-proBNP= N-terminal prohormone of B-type natriuretic peptide; WOCBP=women of childbearing potential.

a The screening visit is only required for Part 1 patients. Assessments collected at Part 2 - Week 48 or Part 2 - Week 52 should be used to assess eligibility for Part 2 patients.

b On Day 1, all required procedures should be performed and eligibility confirmed before study drug is dispensed in the extension.

c Adverse event assessments on Day 1 should be performed following study drug administration.

d For patients enrolled in Part 2 of the study, visit procedures required at Week 52 and also Extension Day 1 should only be performed once since Part 2 Week 52 and Extension Day 1 should occur on the same day.

e For patients with echocardiograms and electrocardiograms collected within 90 days prior to the Screening Visit, the most recent echocardiogram and electrocardiogram can be used to assess patient eligibility.

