**9.9.16. Hematology**

Blood samples will be collected for hematology assessments at the times indicated in [Table 3](#), [Table 4](#), and [Table 5](#). Hematology assessments are listed in [Table 7](#). Every effort should be made to collect laboratory data using the central lab. Where use of the central lab is not possible, laboratory assessments should be collected through a local lab and reviewed by the investigator. As noted in [Table 7](#), HbA1c will only be collected at Screening and Week 12 visits.

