**Table 7: Hematology Assessments**

Hematology Assessments
Hematocrit
Hemoglobin
HbA1C (Screening, Week 12)
Red blood cell (RBC) count
White blood cell (WBC) count
Neutrophils
Bands (if detected)
Lymphocytes
Monocytes
Basophils (if detected)
Eosinophils (if detected)
Absolute platelet count
Mean corpuscular hemoglobin (MCH)
Mean corpuscular volume (MCV)
Mean corpuscular hemoglobin concentration (MCHC)
Reticulocyte count

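### Eosinophilia above 5% with ALT or AST above 3X ULN forces a permanent stop, but the repeat testing in Protocol 9.1.1 never measures eosinophils

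*Protocol*

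**What the plan says.** **The stop.** Protocol 8.5.1 introduces its liver criteria with "Patients must permanently discontinue study drug if any of the following occur", and 9.1.1 repeats the same four rules:

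- ALT or AST above 8X ULN;
- above 5X ULN for more than 2 weeks;
- above 3X ULN with total bilirubin (TBL) above 2X ULN;
- above 3X ULN with the appearance of any of a list of symptoms and signs, the last of which is eosinophilia above 5%.

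**The follow-up.** When ALT or AST exceeds 3X ULN, 9.1.1 says "Transaminase levels (as well as TBL, GGT, ALP) will be checked within 48 to 72 hours during an unscheduled visit". It continues: "Testing will be repeated every 72 to 96 hours until transaminase levels are below 3X the ULN for at least one week", or until consent is withdrawn. No other analyte is named. On further work-up, 9.1.1 says only "Additional tests/studies may be warranted depending on the clinical presentation".

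**Where eosinophils are measured.** They are listed in Table 7 (hematology), not Table 6 (chemistry). Section 9.9.16 sets the timing: "Blood samples will be collected for hematology assessments at the times indicated in" Tables 3, 4 and 5, which are the visit schedules. In the extension (Table 5), on-treatment hematology falls at Weeks 4, 10, 16 and 24, then every 24 weeks.

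**The concern.** A mandatory stop depends on a laboratory value that the follow-up of the triggering event does not collect. The symptoms and physical signs on the list can be asked about or examined at each unscheduled visit. Eosinophilia without symptoms cannot be seen without a differential count. Section 9.1.1 itself expects almost all transaminase elevations to be asymptomatic, so the laboratory criteria carry much of the weight.

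A patient can also remain on drug in this state. Between 3X and 5X ULN no level-based stop applies, whatever the duration. Between 5X and 8X ULN it applies only after more than 2 weeks. What is at stake is patient safety: dosing could continue after the protocol's own criterion for permanent discontinuation has been met.

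**Working it through.** The plan gives no figure to reproduce here. The check has three steps.

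**1. Each stopping rule against the repeat panel (ALT, AST, TBL, GGT, ALP)**

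| Rule | Needs | Available at each repeat? |
|---|---|---|
| > 8X ULN | ALT, AST | Yes |
| > 5X ULN for more than 2 weeks | ALT, AST over time | Yes |
| > 3X ULN and TBL > 2X ULN | ALT, AST, TBL | Yes |
| > 3X ULN with a clinical symptom or sign | History and examination | Yes, at the visit |
| > 3X ULN with eosinophilia > 5% | Differential count | **No** |

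Eosinophilia is the only laboratory criterion that the panel does not serve. Chemistry and hematology share the same scheduled on-treatment visits in Table 5. Eosinophilia already present in a scheduled triggering sample is therefore found; the gap concerns what appears afterwards.

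**2. Time to the next scheduled on-treatment hematology (extension, Table 5)**

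Inputs: Days 28, 70 and 112, each ±3 days; Days 168, 336, 504 and so on, each ±14 days. Interval = difference in nominal days ± the sum of the two windows.

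- Day 28 to 70, and 70 to 112: 42 ± (3 + 3) = 36 to 48 days
- Day 112 to 168: 56 ± (3 + 14) = 39 to 73 days
- Day 168 to 336, and later: 168 ± (14 + 14) = 140 to 196 days

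**3. Required repeat draws during an elevation**

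The documents do not say how long elevations last, so 14 and 28 days above 3X ULN, counted from a scheduled draw at Week 4 or later, are assumed. Slowest schedule: first repeat at 72 hours, then every 96 hours (days 3, 7, 11, ...). Fastest: first at 48 hours, then every 72 hours (days 2, 5, 8, ...). The required week below 3X ULN runs from the first draw below 3X, and that draw is counted.

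| Elevation | Schedule | Draws above 3X | Draws below 3X | Total |
|---|---|---|---|---|
| 14 days | Slowest | days 3, 7, 11 = 3 | days 15, 19, 23 = 3 | 6 |
| 14 days | Fastest | days 2, 5, 8, 11, 14 = 5 | days 17, 20, 23, 26 = 4 | 9 |
| 28 days | Slowest | days 3, 7, ..., 27 = 7 | days 31, 35, 39 = 3 | 10 |
| 28 days | Fastest | days 2, 5, ..., 26 = 9 | days 29, 32, 35, 38 = 4 | 13 |

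The shortest hematology interval, 36 days, exceeds 28 days. No scheduled hematology falls inside either assumed elevation, so the number of required eosinophil values while above 3X ULN is 0, against 3 to 5 (14 days) or 7 to 9 (28 days) liver panels.

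**The case against.** The strongest reply is that little is left uncovered and that what remains may be handled elsewhere.

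- **Investigators may add tests.** Section 9.1.1 allows for further tests, 9.6 lists additional laboratory tests as a reason for an unscheduled visit, 12.6 has drug-related abnormal results followed to resolution, and the DSMB reviews laboratory data. This lowers the chance of a miss. But 9.1.1 and 9.6 are permissive, 12.6 concerns results already observed, and the DSMB can review only values that were collected. None of them requires a differential.
- **Unseen documents.** Section 9.1.1 refers to the Investigator's Brochure for more information on these elevations, and Appendix 13 (section 4.1) shows that the Brochure contains investigator guidance on them. A wider repeat panel could be specified there or in the laboratory manual. This stands as a limit on the conclusion.
- **The intervals are not time at risk.** Correct. The rule cannot be met below 3X ULN, so exposure lasts only as long as the elevation: at most 14 or 28 days under the assumptions. The protocol calls the increases transient. The 36- to 196-day intervals show only that no scheduled draw falls within that time.
- **More counts, more false stops.** A 5% threshold with a permanent consequence could remove a patient whose eosinophils are raised by allergy or have long been high, in a disease for which the protocol says there is no effective therapy. This cost is real and cannot be sized from the documents. It follows from the sponsor's own rule, which applies whenever a count happens to be taken.

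**Conclusion.** The concern holds on the protocol text. A site following 9.1.1 to the letter can miss a discontinuation that 8.5.1 and 9.1.1 make mandatory. The uncovered case is specific: isolated eosinophilia above 5%, first appearing after the triggering sample, while ALT or AST stays above 3X ULN, with no listed clinical sign and no other stopping rule met.

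No event rate is claimed, because the documents give neither the frequency of elevations above 3X ULN nor that of later eosinophilia. The draw counts rest on the assumed 14- and 28-day durations. Parts 1 and 2 are complete according to Appendix 13, so a change now helps only patients in the open-label extension and leaves the primary endpoint, power and type I error untouched. Confidence is moderate because the Brochure and laboratory manual could not be checked. The change is still worth making: the gap is small, but it concerns patient safety and costs little to close.

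**What to change.** In 9.1.1, add a complete blood count with differential (eosinophil percentage) to the 48 to 72 hour check and to each later repeat. While ALT or AST is above 3X ULN, a required eosinophil result would then follow within 2 to 3 days of the trigger and every 3 to 4 days after that.

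Leave the stopping rule unchanged, so that eosinophilia in the triggering sample still counts. If the sponsor wants a reference for *appearance*, use the pre-treatment value rather than the triggering draw; this would also limit stops for longstanding eosinophilia. If the Brochure or laboratory manual already requires the differential, a cross-reference in 9.1.1 is enough.

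**Cost.** One line of text, and an assumed one extra tube at draws already required: 6 to 9 tubes for a 14-day elevation or 10 to 13 for 28 days, including the week below 3X ULN. The differential could instead end at the first draw back below 3X ULN and resume on a rebound. That leaves 3 + 1 to 5 + 1 = 4 to 6 tubes (14 days), or 7 + 1 to 9 + 1 = 8 to 10 (28 days). The trade-off to accept is some risk that incidental eosinophilia, for example from allergy, forces a permanent stop.

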## 9.2. Prior and Concomitant Medications

### 9.2.1. Excluded Medications

Patients who have taken any of the following drugs within 30 days prior to Study Day 1 will be excluded from the study:

- Any other investigational drug
- Anticoagulant therapy, with the exception of a daily baby aspirin (up to 81 mg)

Patients who have taken any of the following drugs within 14 days prior to Study Day 1 will be excluded from Part 1 and Part 2:

- Antioxidant supplements, including but not limited to idebenone, coenzyme Q10, nicotinamide, and dosages exceeding the recommended daily allowance of vitamin E
- Anti-spasticity agents

Patients who have taken any of the following drugs within 7 days prior to Study Day 1 will be excluded from the study:

- Herbal preparations, minerals, or over-the-counter medication, except as identified in Section [9.2.2](#)
- Sensitive substrates for cytochrome P450 2C8 or 3A4 (e.g., repaglinide, midazolam, sildenafil)
- Moderate or strong inhibitors or inducers of cytochrome P450 3A4 (e.g., carbamazepine, phenytoin, ciprofloxacin, grapefruit juice)
- Substrates for p-glycoprotein transporter (e.g., ambrisentan, digoxin)

The following medications and medication classes are not permitted during Part 1 and Part 2, except as noted in Section 9.2.2:

- Anticoagulant therapy, with the exception of daily baby aspirin (up to 81 mg)
- Antioxidant supplements, including but not limited to idebenone, coenzyme Q10, nicotinamide, and dosages exceeding the recommended daily allowance of vitamin E
- Herbal preparations, vitamins, minerals, or over-the-counter medication, except as identified in Section 9.2.2
- Sensitive substrates for cytochrome P450 2C8 or 3A4 (e.g., repaglinide, midazolam, sildenafil)
- Moderate or strong inhibitors or inducers of cytochrome P450 3A4 (e.g., carbamazepine, phenytoin, ciprofloxacin, grapefruit juice)
- Substrates for p-glycoprotein transporter (e.g., ambrisentan, digoxin)
- Any interventional therapy intended to treat the Friedreich's ataxia disease condition, with the exception of a constant exercise regimen
- Anti-spasticity agents

The following medications and medication classes are not permitted during the extension study

- Sensitive substrates for cytochrome P450 2C8 or 3A4 (e.g., repaglinide, midazolam, sildenafil)
- Moderate or strong inhibitors or inducers of cytochrome P450 3A4 (e.g., carbamazepine, phenytoin, ciprofloxacin, grapefruit juice)
- Substrates for p-glycoprotein transporter (e.g., ambrisentan, digoxin)

### **9.2.2. Permitted Medications**

The following concomitant medications are permitted, as authorized by the treating physician:

- Antibiotics, except as noted above (Section 9.2.1)
- Daily multivitamin
- Pain medication, except as noted above (Section 9.2.1)
- Other medications intended to manage concurrent diseases, except as noted above (Section 9.2.1)
- Oral, implantable, or injectable contraceptives

The following concomitant medications are permitted only during the extension study:

- Antioxidant supplements, including but not limited to idebenone, coenzyme Q10, nicotinamide, and dosages exceeding the recommended daily allowance of vitamin E
- Anti-spasticity agents

Patients taking medication chronically should be maintained on those same doses and dose schedules throughout the study period, as medically feasible. Patients taking medications with intermittent or as-needed schedules should try to avoid taking the concomitant medication on days when PK samples will be collected, as medically feasible.

### **9.3. Compliance with Study Drug**

The investigator or designee will only dispense study drug to patients randomized to study treatment in accordance with the protocol. The study drug must not be used for reasons other than that described in the protocol.

All patients will return all bottles and unused pills and will be dispensed a new kit of study drug at visits indicated in [Table 3](#), [Table 4](#), and [Table 5](#). In addition, patients in the first cohort of Part 1 will return all unused pills at the Week 2 visit and will be dispensed a new kit of study drug at that time. Compliance will be measured by counting pills to determine the number of missed doses from one visit to the next. Patients will also be provided a dosing diary to document that pills were taken as instructed as well as the date and time of dosing (Section 9.9.23). To be considered compliant with study drug, patients can miss no more than 25% of the total planned doses (i.e., 21 doses during Part 1, or 84 doses during Part 2) during the study. Patients who exceed the number of allowed missed doses will be considered noncompliant with dosing. Patients will not be discontinued from the study drug nor terminated

from the study for noncompliance, but protocol deviations should be recorded for dosing noncompliance.

#### **9.4. Randomization**

Patients enrolled in Part 1 cohorts will be randomized 3:1 to RTA 408 at the cohort-specific dose level or placebo. Patients enrolled in Part 2 will be randomized 1:1 to RTA 408 150 mg or placebo. Randomization in Part 2 will be stratified by pes cavus status (pes cavus vs. no pes cavus). Patients with pes cavus, a musculoskeletal foot deformity characterized by high arch of the foot that does not flatten with weight-bearing, will not comprise more than 20% of patients enrolled in Part 2. Randomization for both Part 1 and Part 2 will be generated using a centralized IWRS.

Patients enrolled in the extension will be assigned to RTA 408 150 mg.

